### **6.4 SUBJECT SETS ANALYSED**

[figure not shown]
- Screened set (SS):  
This subject set includes all subjects who signed informed consent.
- Randomised set (RS):  
This subject set includes all randomised subjects, whether treated or not.
- Treated set (TS):  
This subject set includes all subjects who were dispensed study medication and were documented to have taken at least one dose of investigational treatment.
- PK parameter analysis set (PKS):  
This subject set includes those subjects in the TS with at least one valid plasma concentration value available.
- 

Table 6.4: 1 Planned analysis per subject set

Class of analysis	Subject set			
	SS	TS	PKS	[REDACTED]
Disposition	X			
Demographic & baseline characteristics		X		X
Safety & treatment exposure		X		
PK			X	
Efficacy		X		
[REDACTED]				

Note that the number of subjects with available data for an endpoint may differ.

## 6.6 HANDLING OF MISSING DATA AND OUTLIERS

In general, missing data will not be imputed. For specific analysis, technical details of missing data handling rules are as follows:

### Primary objective analysis

Missing or incomplete AE dates are imputed according to BI standards ([9.5](#)).

### Secondary objective analysis

- Missing data will not be imputed for biomarker endpoints. BLQ is not considered as missing data, however, it will be imputed as half of Lower Limit of Quantitation (LLOQ).
  - Missing data and outliers of PK data are handled according to BI standards ([9.6](#)).
-

## **6.7 BASELINE, TIME WINDOWS AND CALCULATED VISITS**

For all parameters (except for biomarkers), baseline is defined as the last non-missing value prior to first administration of trial medication, or on the same date of first drug administration, if assessment times are not collected (e.g., vital signs, laboratory tests).

For specific assessments, multiple measurements are planned prior to first drug intake (e.g., at Visit 1 or 2). To derive the baseline, specific rules will apply as shown in [Table 6.7: 1](#).

According to CTP Section 5.4.1.3.2 Sputum sample collection at site, if sputum samples do not meet the sputum collection criteria as defined in the ISF/Lab Manual, it is generally possible that the patient returns the next day to provide the sputum sample. Baseline sputum measurement could be on or prior to the first drug administration + 1 day.

Table 6.7: 1 Derivation of baseline for assessments with multiple measurements prior to first drug administration

Parameter	Baseline value derivation
Biomarkers based on sputum	Mean of all available valid measurements collected up to date of first study drug administration + 1 day
Murray sputum colour chart	Last valid measurement collected up to date of first study drug administration + 1 day
NEATstik®	Mean of all available valid samples collected up to date of first study drug administration + 1 day

Measurements taken after first administration of trial treatment will be considered either on- or off-treatment values based on the definition in [Table 6.1.1: 1](#). Visit windowing will be performed as described in the tables below, in order to assign data to the relevant study visit based on the actual day of the assessment. Data will be analyzed using the re-calculated visits in the statistical tables. However, in the listings, all visits performed will be displayed (even if outside time-window), along with the re-calculated visit. The date of first treatment intake will be used as Study Day 1 for the time windowing. If more than one value is available within one time window the one which is closest to the planned time/day is used for analysis. In case two values are equidistant from the planned time/day, then the last one will be picked.

Analysis of AE data (including findings in 12-lead ECG assessments or physical examinations), potentially clinically significant abnormal laboratory values, concomitant medication or non-drug therapies will not be based on visits and thus no assignment to time windows is necessary. For this type of data, a safety analysis ‘on-treatment’ concept will be used depending on their actual onset dates.

Table 6.7: 2 Time windows for assignment of safety assessment – laboratory

[figure not shown]
Visit number (CTP)	Visit label (analysis)	Planned Day	Time window [days]		
			Window per CTP	Start (analysis)	End (analysis)
V1	Screening	-42	≥7d prior to V2	All pre-baseline measurements	
V2	Baseline	1	± 0	NA	Date/time of first administration of study drug
V3	Week 1	8	± 3	Start of on-treatment phase 	18
V4	Week 4	29	± 3	19	43
V5	Week 8	57	± 3	44	71
V6	Week 12	85	± 3	72	End of on-treatment phase 
EoS	Follow-up	113	+ 7	All post-treatment measurements after last drug intake + REP	

 As defined in [table 6.1.1: 1](#).

Table 6.7: 3 Time windows for assignment of biomarkers assessed in sputum

Visit number (CTP)	Visit label (analysis)	Planned Day	Time window [days]		
			Window per CTP	Start (analysis)	End (analysis)
V1	Screening	-42	≥7d prior to V2	All pre-baseline measurements	
V2	Baseline	1	± 0	NA	Date/time of first administration of study drug
V3	Week 1	8	± 3	Start of on-treatment phase 	18
V4	Week 4	29	± 3	19	43
V5	Week 8	57	± 3	44	71
V6	Week 12	85	± 3	72	Last drug administration
EoS	Safety Follow-up	Last drug administration + 28		All measurements after last drug administration + 1	All measurements before last drug administration + 36

 As defined in [table 6.1.1: 1](#).

Proprietary confidential information © 2024 Boehringer Ingelheim International GmbH or one or more of its affiliated companies.

For all variables with a sparse sampling schedule that does not match the schedules in the above tables, the screening, baseline and follow-up phase will follow the same rules, while the start and end days of the on-treatment time windows will be equidistant from the planned visit day.

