However, BI 1291583 exhibits moderate to high solubility over GI tract pH range. In combination with the high permeability found in CaCo-2 cells, BI 1291583 is classified as a BCS class I compound. These physico-chemical characteristics support an expectation of similar PK profiles across non-GI diseases. BI 1291583 at a dose level of 5 mg qd is fully soluble in the gastric volume irrespective of pH. No difference in relative bioavailability was observed in healthy volunteers under fed and fasted conditions (study 1397-0008, [REDACTED] BI 1291583, high-fat and high caloric meal). Due to the absence of a pH dependent absorption, a difference in exposure for patients with CF is considered unlikely. The sampling regimen with two full profiles on Day 1 and at steady state on Day 85, allows to characterise the absorption as well as the initial elimination and distribution phase. Additional trough samples especially before steady state (before 2 weeks) will provide information on the accumulation profile of BI 1291583. Overall, trough samples serve a better characterisation of clearance in CF patients. Together with PK information from Phase I and Phase II studies, the PK sampling regimen may enable identification of covariate effects in case there are differences between the different study populations.

A 28-days follow-up period without treatment covers the residual effect period during which BI 1291583 exposures are expected to return to levels below quantification and after which pharmacodynamic effects are expected to have reversed.

There is currently no approved pharmacotherapy available to treat the inflammatory component of BE in CF patients. Thus, no active control group is included in the trial. To mitigate the potential risk associated with a placebo-controlled trial in this patient population, usual SoC will be allowed as stable background treatment or in case of complications of CF.

To ensure safety of trial participants, an independent DMC will conduct regular reviews of the trial safety data.

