4.1.4 Drug assignment and administration of doses for each trial participant

A double-blind design is required to keep the blind (see [Section 4.1.5](#)) of trial participants and investigators. Patients will receive bottles containing 20 tablets each of either active or placebo. Once a day, they will take one tablet for 12 weeks.

The patients should swallow the trial medication unchewed together with a glass of water (~250 mL). Trial medication should be taken at the same time each morning (e.g., 8:00 am) during the treatment phase, within a time window of +/- 1 hour. Missed dose(s) will not be replaced. If a dose is missed by more than 12 hours, that dose should be skipped, and the next dose should be taken as scheduled.

No restrictions apply whether to take the medication with food or close to a meal as no food effect was observed in clinical Phase I.

On visit days, trial medication will be taken at the site from the new kits assigned at the respective visits, even if outside the normal schedule to accomplish assessments at the site. Patients will then return to their usual intake time.

The last dose will be administered at EOT.

The investigational product should only be dispensed to participating patients by authorised personnel as documented in the ISF.

The kits will be used for treating the patient at visits at the site and at the respective time points at home in between site visits.

In the event of force majeure or other disrupting circumstances (e.g. pandemic, war, please see [Section 6](#)) physical visits to the sites may not be feasible or may need to be restricted to ensure participant safety. Based on a thorough assessment of benefits and risks, the investigator may still decide to continue the trial treatment. Where permitted by local law and regulations, trial medication may be shipped directly to the participants' home.

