## 6. GENERAL ANALYSIS DEFINITIONS

### 6.1 TREATMENT(S)

#### 6.1.1 Analysis phases

For safety analyses, data collected between first drug intake up to the end of residual effect period (REP) will be considered as “on-treatment” period for the evaluation.

Table 6.1.1: 1 Analysis phases

Study analysis phase	Label	Start (included)	End (excluded)
Screening	Screening	Date of informed consent at 12 a.m.	Date/time of first drug administration
Treatment	Placebo BI 5 mg respectively	Date/time of first administration of study drug	12:00 a.m. on day after last drug administration, or 12:00 a.m. on day after last contact date (whichever occurs first)
Residual effect period	Residual effect period	12:00 a.m. on day after last administration of study drug	12:00 a.m. on day after last administration of study drug + REP (28 days)
Follow-up 	Follow-up	12:00 a.m. on day after last administration of study drug + REP (28 days)	12:00 a.m. on day after last contact date

 This phase exists only in those subjects whose last contact date is more than 28 days after last trial drug administration.

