## **7.8.2 Laboratory data**

The analyses of laboratory parameters will be descriptive in nature and will be based on the BI guidance “Handling, Display and Analysis of Laboratory Data” ([9.10](#)).

For continuous safety laboratory parameters, normalized values will be derived. Normalization means transformation to a standard unit and to a standard reference range. The process of normalization, handling of repeat values at the same visit for by-visit displays, as well as standard analyses for safety laboratory data are described in the BI guidance. All analyses considering multiple times of the ULN will be based on standardized values. For continuous safety laboratory parameters, differences to baseline will be calculated.

Only subjects with at least one available post-baseline value will be included in the analysis of an individual laboratory parameter. All individual laboratory data will be listed. Values outside of the normal reference range will be flagged.

For quantitative safety laboratory parameters, descriptive statistics of laboratory values over time and change from baseline will be based upon normalized values and provided by analysis visit, including summaries of the last value on treatment, the minimum value on treatment and maximum value in the treatment period.

Potentially clinically significant abnormalities will be identified based on BI standard rules which are based on standardized lab values, i.e., using SI units. Frequency tables will summarize the number of subjects with potentially clinically significant abnormalities.

Subjects having an abnormal lab value at baseline will be presented in a listing separately. A separate listing will present all subjects with potentially clinically significant lab values. In addition, a summary table will be prepared for the values outside of the clinically significant reference range including frequency and percentage of subjects with abnormal values for will be presented by treatment group.

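### SAP Table 6.7: 2 shuts a Day 113 end-of-study lab out of its own Follow-up window, and Table 6.7: 3 leaves the day after the last dose in no sputum window

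*SAP*

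**What the plan says.** **Phases.** SAP section 6.1.1 treats safety data from first intake to the end of the REP as on-treatment. The REP ends at midnight opening the day after last dose + 28 days. The footnote on the Follow-up phase agrees: "This phase exists only in those subjects whose last contact date is more than 28 days after last trial drug administration".

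**Lab windows.** In SAP Table 6.7: 2, Week 12 runs from Day 72 to "End of on-treatment phase", with a footnote pointing to Table 6.1.1: 1. The Follow-up row has planned day 113 (+7) and admits "All post-treatment measurements after last drug intake + REP". If a window holds several values, the one closest to the planned day is used.

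**Lab summaries.** SAP section 7.8.2 plans by-visit statistics, "including summaries of the last value on treatment, the minimum value on treatment and maximum value in the treatment period".

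**Sputum windows.** Table 6.7: 3 ends Week 12 at the last drug administration. It opens the end-of-study (EoS) window for measurements after last drug administration + 1.

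**Visits.** Protocol section 4.1.4 states "The last dose will be administered at EOT", planned for Day 85. The Flow Chart sets EoS 28 (+7) days after the end-of-treatment (EoT) visit and makes the EoS lab optional. Patients who stop early have EoT as soon as possible and EoS 28 (+7) days after that. Protocol sections 5.4.1.3.2 and 6.1 allow sputum to be given the day after a visit.

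**The concern.** A visit window should contain its own planned day. The lab Follow-up row does not: Day 113 is the last day of the REP, and the row starts only after the REP. One day's difference in the visit date then changes both the visit label and the phase of a lab value.

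Three outputs could mislead:

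- the Follow-up row of the by-visit lab table, which would omit patients seen exactly on the planned day;
- the last on-treatment summary, which could carry a value taken 28 days off drug;
- the weekly rows, which could carry off-drug values from early stoppers, who have no Day 85 value to displace them.

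With 16 active and 8 placebo patients planned, one or two such values are visible in a summary row. Sputum has a related gap: a Week 12 sample given the next day, as the protocol allows, belongs to no window.

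**Working it through.** **Inputs.** REP 28 days (SAP 6.1.1); planned days 8, 29, 57, 85 and 113 (Table 6.7: 2); last dose at EoT (protocol 4.1.4); EoS at EoT + 28 (+7) days (Flow Chart).

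**Planned figures.** EoS = 85 + 28 = Day 113, which matches the table. The other cut-offs are midpoints of planned days: (8 + 29)/2 = 18.5 for 18/19; (29 + 57)/2 = 43 for 43/44; (57 + 85)/2 = 71 for 71/72. The midpoint for the last pair is (85 + 113)/2 = 99, and the table does not use it.

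**Assignment rule.** For last dose on Day L and a lab on Day t:

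- on-treatment if t ≤ L + 28;
- Week 12 if 72 ≤ t ≤ L + 28;
- Follow-up if t > L + 28.

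**Completers.**

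| Last dose | Last REP day | Lab on Day 113 | First Follow-up day | EoS exactly 28 days after last dose |
|---|---|---|---|---|
| 82 | 110 | Follow-up | 111 | Day 110: Week 12 |
| 85 | 113 | Week 12 | 114 | Day 113: Week 12 |
| 88 | 116 | Week 12 | 117 | Day 116: Week 12 |

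For L = 85, the Day 85 lab is 0 days from plan and the Day 113 lab is 28 days away, so Day 85 takes the Week 12 slot. Day 113 then appears in neither row, yet it is the latest value in the on-treatment period. When EoT is the day of the last dose, EoS may fall 28 to 35 days later, and one of those eight days (exactly 28) is hit. If EoS is instead counted from Day 1 (protocol 6.1) and the last dose is on Day 88, Days 113 to 116 are hit.

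**Early stoppers.** An off-drug lab can be labelled Week 12 for any last dose from Day 44 (44 + 28 = 72) to Day 81. The lower windows have no cap at the last dose either.

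| Last dose | Lab | Days off drug | Label now |
|---|---|---|---|
| 10 | EoS on Day 38 | 28 | Week 4 |
| 40 | EoS on Day 68 | 28 | Week 8 |
| 50 | EoS on Day 78 | 28 | Week 12 |
| 60 | EoS on Day 88 | 28 | Week 12 |
| 70 | Delayed EoT on Day 73 | 3 | Week 12 |

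The EoS rows require EoT on the day of the last dose. If the patient who stops on Day 50 has EoT on Day 51, EoS is Day 79 at the earliest. That is past 50 + 28 = 78, so it is Follow-up.

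**Other reading of the footnote.** Table 6.1.1: 1 has no phase named on-treatment. If the footnote means the Treatment phase alone, labs on Days 86 to 113 fit no window. Day 113 is still not Follow-up.

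**Sputum.** Week 12 ends on Day L and EoS starts after Day L + 1, so Day L + 1 is uncovered. If the EoS start is read as including Day L + 1, a next-day Week 12 sample is labelled Safety Follow-up. Neither reading puts it in Week 12.

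**Check of the fix (Follow-up if t > L + 14).** For L = 85, Follow-up starts on Day 100, the day after the midpoint of 99. For L = 82 and 88 it starts on Days 97 and 103, so every EoS day in the table above is Follow-up. Among the early stoppers, Days 38, 68, 78 and 88 exceed 24, 54, 64 and 74 and become Follow-up. The delayed EoT on Day 73 does not exceed 84 and stays in Week 12.

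**The case against.** Counting the REP as on-treatment is deliberate. Both documents state it, and protocol sections 1.2 and 3.2 justify it by the slow reversal of the pharmacodynamic effect. This stands: the REP rule itself is sound for adverse events and worst values. The defect is confined to visit labels and the last on-treatment summary.

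The number affected is small. EoS labs are taken at the investigator's discretion, mostly only an EoS exactly 28 days after the last dose is hit, and early stoppers' EoS often falls beyond the REP. This also stands.

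Nothing is hidden. All lab data are listed with actual and re-calculated visits, minimum and maximum values are summarised, and clinically significant abnormalities are not assigned to windows. This stands for individual values but does not correct the rows concerned.

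Lab and sputum tables may reasonably use different cut-offs. That is fair, and the difference alone is no error. The sputum gap stands as a separate point.

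A cut at last dose + 1 day would be a poor remedy for labs. It would move an early stopper's delayed EoT lab into Follow-up and, without a precedence rule, leave the Week 4 and Week 8 windows uncapped. This is accepted, and the fix below avoids it.

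**Conclusion.** The tables are wrong as written, with minor consequences. For a last dose on Day 85, an EoS lab on Day 113 is excluded from Follow-up under either reading of the footnote. That it falls in Week 12 and can be summarised as the last on-treatment value rests on applying the section 6.1.1 safety definition. The internal laboratory guidance that the SAP cites might define that summary differently, and it is not available here. The primary endpoint does not use these windows, and the Week 8 neutrophil elastase and PK endpoints of completers are unaffected.

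Three stronger readings are not supported:

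- **Every completer is misassigned.** Only those with an optional EoS lab on an affected day are.
- **The last on-treatment value will show a recovered abnormality.** The documents do not say why investigators would take an EoS lab, or what it would show.
- **Mandatory EoS vital signs are equally affected.** SAP section 7.8.3 refers to section 6.7 for windows, but the public text does not say which table applies. It is worth checking, but is not counted here.

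**What to change.** 1. In Table 6.7: 2, for by-visit displays, end Week 12 at last drug intake + 14 days and start Follow-up after that. State that Follow-up takes precedence over any Week 1 to Week 12 window. This covers early stoppers and keeps an EoT lab delayed by up to 14 days in its treatment week.
2. Use the same cut-off for the last value on treatment.
3. Keep last dose + REP for treatment-emergent adverse events, minimum and maximum values, and tables of potentially clinically significant abnormalities.
4. In Table 6.7: 3, end Week 12 at last drug administration + 1 day.
5. Correct the footnote so that it points to a defined on-treatment phase.

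The cost is a short text edit with matching programming, and no change to data collection. The downside is that visit tables and adverse-event or abnormality tables will use different cut-offs, which needs a footnote. Labs up to 14 days off drug can still carry a weekly label; that is the price of keeping delayed EoT labs.
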